13. DATA PRESERVATION.....	38
14. MODIFICATION OF THE SCHEME.....	38
15. ORGANIZATION AND MANAGEMENT OF TESTS.....	38
15.1 PROGRESS AND ARRANGEMENT OF TEST WORK.....	39
SIGNATURE PAGE FOR PARTICIPATING CENTER RESEARCHERS	40
BIDDER'S SIGNATURE PAGE	41
INSPECTOR'S SIGNATURE PAGE	44
ENCLOSURE 1 CORONARY HEART DISEASE SUBJECT SPORTS MANUAL CORONARY HEART DISEASE SUBJECT SPORTS MANUAL	46

Abbreviation

Abbreviation	English full name	Chinese
AE	Adverse Event	不良事件
ALP	Alkaline Phosphatase	碱性磷酸酶
ALT	Alanine Aminotransferase	丙氨酸氨基转移酶/谷丙转氨酶
AST	Asparate Aminotransferase	门冬氨酸氨基转移酶/谷草转氨酶
BUN	Blood Urea Nitrogen	尿素氮
CFDA	China Food and Drug Administration	国家食品药品监督管理总局
HCY	Homocysteine	血同型半胱氨酸
Cr	Creatinine	肌酐
CRF	Case Report Form	病例报告表
CRO	Contract Research Organization	合同研究组织
FAS	Full Analysis Set	全分析集
GCP	Good Clinical Practice	药物临床试验质量管理规范
GGT/ γ -GT	γ -Glutamyl Transpeptidase	谷氨酰转肽酶
ITT	Intention to Treat	意向性治疗
PPS	PerProtocol Set	符合方案集
QA	Quality Assurance	质量保证
QC	Quality Control	质量控制
SAE	Serious Adverse Event	严重不良事件
SOP	Standard Operating Procedures	标准操作程序
SS	Safety Analysis Set	安全性数据集

Clinical trial scheme of Xinnaoning capsule • Abstract

Title	To evaluate the efficacy and safety of Xinnaoning Capsule in treating chronic stable angina pectoris (Qi stagnation and blood stasis syndrome) with placebo as control: a randomized, double-blind, parallel controlled, multi-center clinical study
Purpose	To evaluate the efficacy and safety of Xinnaoning Capsule in the treatment of chronic stable angina pectoris (Qi stagnation and blood stasis syndrome)
Experimental design	A randomized, double-blind, placebo-controlled, multi-center, efficacy test design is used.
Subject population	Subjects with chronic stable angina pectoris (qi stagnation and blood stasis syndrome)
Inclusion Criteria	
1. Refer to the Guidelines for Diagnosis and Treatment of Chronic Stable Angina issued by the Chinese Medical Association in 2007, 2012 ACP/ACCF/AHA/AATS/PCNA/STS (Guidelines for Diagnosis and Management of Stable Ischemic Heart Disease: American Heart Foundation/American Heart Association/American Medical Association/American Thoracic Surgery Association/American Association for Cardiovascular Preventive Nursing/American Association for Cardiovascular Angiography and Intervention/American Thoracic Association The Diagnosis of Stable Ischemic Heart Disease: Guidelines for Clinical Practice, Guidelines for the Management of Stable Coronary Artery Diseases in 2013 ESC, which can diagnose coronary heart disease in accordance with any of the following:
 
(1) Has a clear history of old myocardial infarction, or PCI history, or bypass history;
 
(2) Coronary angiography (results indicate at least one coronary artery stenosis with stenosis (>50%) or coronary CTA suggests stenosis with stenosis (>50%).
 
2. Those who met the diagnostic criteria of chronic stable angina pectoris: those who had a history of angina pectoris more than 1 month and had no significant changes in the degree, frequency, nature and inducing factors of angina pectoris;
 
3. The severity of angina pectoris of the Canadian Cardiovascular Society (CCS) was classified as Grade I to Grade III, and angina pectoris occurred more than twice a week.
 
4. The syndrome differentiation of TCM is Qi stagnation and blood stasis syndrome.
 
5. Age ranges from 30 to 79 years old.

	6. Sign the informed consent.
Exclusion Criteria	
 1. Severe cardiopulmonary insufficiency (grade III, IV, severe abnormal pulmonary function); 2. Poor control of hypertension (systolic blood pressure (> 160 mmHg) or diastolic blood pressure (> 100 mmHg) after treatment; 3. Complicated with liver and kidney function damage, ALT, AST (> 1.5 times of the upper limit of normal value), or Cr (> the upper limit of normal value), combined with hematopoietic system and other serious primary diseases; 4. Acute myocardial infarction within 3 months after interventional therapy; 5. Cardiac pacemaker; 6. Pregnancy, lactation or pregnancy planning; 7. Anaphylactic constitution or allergic to known ingredients of research drugs; 8. Chest pain caused by other causes (moderate anemia, hyperthyroidism, etc.) 9. Those who participated in other clinical drug trials within one month; 10. According to the judgement of the researchers, it is not advisable to participate in clinical researchers. 11. Other factors affecting ST-T changes in ECG, such as myocardial hypertrophy, left bundle branch block, etc.
Sample size	
According to the statistical requirements, the sample size was estimated. The main effect index was the curative effect of angina pectoris symptoms treated for 12 weeks. According to the literature, the total effective rate of basic treatment plus placebo was 67.5%, and the total effective rate of basic treatment plus experimental drugs was predicted to be 84.3%. set $\alpha=0.05$, $1-\beta=0.2$, according to the experimental group: control group = 1:1 set up group,
 $n = \frac{P_1 \times (100 - P_1) + P_2 \times (100 - P_2)}{(P_2 - P_1)^2} \times f(a, b)$ 
The minimum sample size to meet the statistical requirements was

	98.4 cases in each group, and the dropping rate was not more than 20%, 120 cases in each group, a total of 240 cases.
Effectiveness evaluating indicator	1. Main outcome measures: The curative effect of angina pectoris; 2. Secondary indicators: curative effect of TCM syndromes, grading changes of severity of angina pectoris, changes of attack times per week, nitroglycerin dosage, score of Seattle Angina Scale and incidence of cardiovascular events, blood HCY (blood homocysteine).
Safety evaluating indicator	1. Possible adverse reaction symptoms. 2. General physical examination items, such as body temperature, pulse, breathing, blood pressure, etc. 3. Laboratory examination: blood routine, urine routine + microscopy, stool routine + Occult blood, liver and kidney function (ALT, AST, ALP, GGT, TBIL, BUN, Cr), blood lipid (HDL-C, LDL-C, TG, CH), blood coagulation.
Dosage regimen	The induction period was 2 weeks and the treatment period was 12 weeks. Introducing period: 2 weeks, time window (+2 days). Introducing drug regimen: Both groups were given Xinnaoning capsule Simulator 3 capsules per time, 3 times per day, orally, after meals. Course of treatment: 12 weeks, time window (+4 days). Test group: Xinnaoning capsule, 3 capsules per time, 3 times per day Control group: Xinnaoning capsule Simulator 3 tablets per time, 3 times per day, oral, after meals.
Combined medication	1. In addition to experimental medication, nitroglycerin tablets can be used to alleviate symptoms when angina attacks. For drugs already used to treat coronary heart disease before inclusion, such as antiplatelet drugs, angiotensin-converting enzyme inhibitors (ACEI) or angiotensin II receptor antagonists (ARB), statins, calcium antagonists, beta-blockers and long-acting nitrates, the original varieties and dosages can be continued without adjustment. During the study period, it is forbidden to add any other Chinese and Western medicines which have therapeutic effects on angina pectoris of coronary heart disease. 2. For the original and emerging diseases requiring drug treatment, the drug combination should be recorded in the medical record and CRF in

	detail, including the generic name of the drug, dosage and method of administration, the starting time of drug use and the reasons for its use.
Course of treatment	The induction period was 2 weeks and the medication period was 12 weeks.
Experimental progress	The preliminary plan is to complete all clinical trials within 18 months from the arrival of the drug in the hospital.

Clinical trial scheme of Xinnaoning Capsule • main body

1. Test background

Coronary heart disease (CHD) is the most harmful cardiovascular disease worldwide. It is also the first cause of hospitalization and death of adult heart disease in China. Its morbidity and mortality are still on the rise. Active treatment and prevention of CHD is an important subject in medical research.

Coronary heart disease angina pectoris is a kind of heart disease caused by myocardial ischemia and anoxia caused by coronary atherosclerosis. It belongs to the category of "chest obstruction" and "heartache" in traditional Chinese medicine. The occurrence of angina pectoris is mostly related to cold pathogenic invasion, improper diet, emotional disorder, old body deficiency and other factors. The pathogenesis of "Chest Bi" is deficiency and reality, which is actually cold coagulation, Qi stagnation, blood stasis, phlegm obstruction, obstruction of chest Yang and heart vein; deficiency is deficiency of heart, spleen, liver and kidney, heart and vein dystrophy. One of its common pathogenesis is stagnation of Qi and blood stasis, blockage of blood vessels, so it should be treated by activating blood circulation and removing blood stasis, dredging channels and collaterals, as well as tranquilizing Qi and tranquilizing spirit, in order to achieve the goal of blood stasis to remove new life and nourish the blood vessels of viscera and viscera.

Xinnaoning Capsule (Z20025697), produced by Guizhou Jingcheng Pharmaceutical Co., Ltd., is mainly composed of Ginkgo biloba leaves, Salvia miltiorrhiza, Ginger fruit, Euonymus microphylla and Allium macrophylla. It has the functions of activating blood circulation, promoting Qi circulation, dredging collaterals and relieving pain. Chest stuffiness, dizziness, vertigo, symptoms: chest tightness, tingling, palpitation restlessness, dizziness and dizziness, as well as coronary heart disease, cerebral arteriosclerosis see the above symptoms. Xinnaoning Capsule has not had any adverse reactions for many years after it was put on the market.

Pharmacological research

Xinnaoning Capsule, in which Ginkgo biloba leaf is the monarch medicine, Ginkgo biloba leaf promotes blood circulation and removes blood stasis, relieves pain, is used for coronary heart disease, angina pectoris and blood stasis syndrome caused by hyperlipidemia. Salvia miltiorrhiza and Ginger fruit are the main medicines. Among them, Salvia miltiorrhiza has good effect on promoting blood circulation and removing blood stasis, cooling blood and tranquilizing mind, and has good effect on all diseases caused by blood stasis, especially on heart and brain blood stasis

syndrome. In addition, *Salvia miltiorrhiza* can cool blood and calm the nerves. It has good effect on palpitation and insomnia in the above diseases. Ginger has the function of dispelling cold in warmth, regulating qi and relieving pain. The combination of the two medicines can not only promote blood circulation, but also regulate qi. Qixing can promote blood circulation and remove blood stasis. *Populus microphylla* and *Allium macrophylla* were used as adjuvants. Effectiveness of *Euonymus microphylla* is promoting qi and blood circulation, dredging collaterals and relieving pain. It is used for chest pain, heart pain and coronary heart disease caused by qi stagnation and blood stasis. The effect of Xiebai can regulate qi, broaden chest, promote Yang and disperse. It is used to treat thoracic paralysis and heartache. "Compendium of Materia Medica" says that it can "treat Shaoyin disease, syncope, diarrhea, and chest pain. These two medicines have the functions of regulating qi, promoting blood circulation and strengthening the functions of activating blood circulation, regulating qi and stasis of other medicines. The above medicines are mainly used to promote blood circulation, supplemented by regulating qi. Regulating Qi helps to promote blood circulation. Promoting blood circulation helps to promote qi circulation, blood stasis, meridians and collaterals, and all kinds of symptoms go by themselves to treat chest pain, stroke, stroke, dizziness and other diseases caused by qi stagnation and blood stasis, blockage of blood vessels.

Modern pharmacology shows that flavonoids and terpene lactones are effective components of *Ginkgo biloba* leaves. Experiments show that flavonoids and terpene lactones are beneficial to blood vessel and brain metabolism and inhibit platelet activating factor. Ginkgolides and ginkgolides can significantly improve the oxygen tolerance of brain cells and enhance local brain flow. Ginkgolides have a strong neuroprotective effect. *Salvia miltiorrhiza* can inhibit platelet aggregation, dilate coronary artery, increase the opening of collateral circulation, improve myocardial hypoxia, and also have good scavenging effect of oxygen free radicals. The experiment of *Zingiber officinale* L. showed that *Zingiber officinale* L. oil could reduce the area of myocardial infarction and the level of serum lactate dehydrogenase after myocardial infarction. It has protective effect on myocardial ischemia. It can also slow down the systolic and diastolic blood pressure, slow down the heart rate and reduce the cardiac output. *Allium sibiricum* can inhibit platelet aggregation and reduce serum lipid peroxide and blood lipid. *Euonymus microphylla* can dilate coronary artery, improve myocardial ischemia and reduce oxygen consumption.

Previous clinical trials

1. To observe the clinical effect of Xinnaoning Capsule on angina pectoris of coronary heart disease of qi stagnation and blood stasis type.

From February 2011 to October 2011, Xinnaoning was observed in 309 Hospital

of PLA. Methods: 182 patients with angina pectoris of qi stagnation and blood stasis type were randomly divided into treatment group (102 cases) and control group (80 cases). The control group was treated with routine treatment group (isosorbide mononitrate tablets, aspirin enteric-coated tablets, 100 mg each time, once a day). The treatment group was treated with routine treatment in the control group. Xinnaoning capsule was taken three times a day for 8 weeks. The results are as follows:

Table1 Comparison of improvement effect of angina pectoris between two groups n (%)

Group	n	Markedly effective	effective	invalid	total effective rate
Test	102	34 (33.3)	52 (51)	16 (15.7)	86 (84.3)
Control	80	26 (32.5)	28 (35)	24 (32.5)	56 (67.5)

There were significant differences between groups. , $P < 0.05$

Table2 Comparison of the curative effect of TCM syndromes improvement between two groups before and after treatment

Symptom	Group	n	ME	effective	invalid	TER (%)
Chest pain	T	102	36	56	12	92 (92.2)
	C	80	19	44	17	63 (78.7)
Chest tightness	T	102	42	50	10	92 (90.2)
	C	80	20	42	18	62 (77.5)
palpitation	T	102	34	54	14	88 (86.2)
	C	80	18	43	19	61 (76.3)
pant	T	102	32	49	21	81 (79.4)
	C	80	20	35	25	55 (68.7)
dizzy	T	102	36	54	12	90 (88.2)
	C	80	15	23	42	38 (47.5)
headache	T	102	32	47	22	79 (77.4)
	C	80	7	27	46	34 (42)

Note: Chest pain, palpitation and other symptoms of the two groups were significantly improved after treatment. The treatment group had significant effect on improving chest tightness, chest pain, dizziness, headache and other clinical symptoms, compared with the control group, $P < 0.01$. T=test group, C=control group, ME= Markedly effective, TER= total effective rate

Table3 Comparison of ECG changes before and after treatment in two groups

Group	n	ME	effective	invalid	TER (%)
T	102	39	38	25	76 (74.5)
C	80	31	27	22	58 (72.5)

Note: After treatment, ECG in both groups improved, but there was no significant difference between the two groups.

The clinical results showed that the total effective rate of angina pectoris in the treatment group was better than that in the control group, especially in improving the symptoms of chest pain, chest tightness, dizziness and headache. There were no significant changes in blood pressure and heart rate before and after treatment, and no obvious adverse reactions during treatment, suggesting that the drug is safe. It is an effective and safe drug for the treatment of coronary heart disease and angina pectoris.

2. Evaluation of Xinnaoning Capsule in the Treatment of Angina Pectoris after Coronary Stent Implantation

From June 2012 to June 2014, the cardiovascular disease center of Xiuyan Hospital, Chinese Academy of Traditional Chinese Medicine was studied. Methods: 160 patients with recurrent angina pectoris after coronary artery stent implantation were randomly divided into treatment group (80 cases) and control group (80 cases). The course of treatment was 8 weeks. Control group: aspirin enteric-coated tablets 100mg, once a day, isosorbide mononitrate tablets 20mg, twice a day, atorvastatin calcium tablets 20mg, once a day. Treatment group: On the basis of the control group, Xinnaoning capsule was added, three capsules each time, three times a day. The results are as follows:

Table 4 Comparison of curative effect of angina pectoris between two groups (%)

Group	ME	effective	invalid	TER
T	28 (35.00)	41 (51.25)	11 (13.75)	69 (86.25)
C	19 (23.75)	30 (37.50)	31 (38.75)	49 (61.25)

Note: Compared with the control group, $P < 0.05$

Table 5 Comparison of curative effect of TCM syndromes between two groups (%)

Group	Chest pain			
	ME	effective	invalid	TER
Test (n=80)	26 (32.50)	45 (56.25)	9 (11.25)	71 (88.75)
Control (n=80)	19 (23.75)	32 (40.00)	29 (36.25)	51 (63.75)

Group	Chest tightness			
	ME	effective	invalid	TER
Test (n=80)	26 (32.50)	46 (57.50)	8 (10.00)	72 (90.00)
Control (n=80)	28 (22.50)	35 (43.75)	27 (33.75)	53 (66.25)

Group	pant			
	ME	effective	invalid	TER
Test (n=80)	24 (32.50)	48 (60.00)	8 (10.00)	72 (90.00)
Control (n=80)	18 (22.50)	34 (42.50)	28 (35.00)	52 (65.00)

Group	palpitation			
	ME	effective	invalid	TER
Test (n=80)	22 (27.50)	48 (60.00)	10 (12.50)	70 (87.50)
Control (n=80)	17 (21.25)	34 (42.50)	29 (36.25)	51 (63.75)

Note: Compared with the control group, $p < 0.05$

Table 6 Comparison of ECG changes after treatment between two groups (%)

Test (n=80)	18 (22.50)	39 (48.75)	23 (28.75)	57 (71.25)
Control (n=80)	16 (20.00)	35 (43.75)	29 (36.25)	51 (63.75)

Note: Compared with the control group, $P < 0.05$

Studies have confirmed that Xinnaoning Capsule has a good clinical effect on angina pectoris patients after coronary artery stent implantation by improving myocardial microcirculation, promoting the opening of collateral circulation, inhibiting platelet aggregation, lowering blood lipid and stabilizing platelet. There were no significant changes in ECG, blood pressure and heart rate before and after treatment, and no obvious adverse reactions during treatment, suggesting that the drug is safe.

For many years after Xinnaoning capsule was put on the market, no adverse reactions were recorded in the literature. This experiment completes the clinical trial of Xinnaoning Capsule in treating chronic stable angina pectoris (Qi stagnation and blood stasis syndrome), and objectively evaluates its clinical efficacy and safety.

2. Experimental purpose

To evaluate the efficacy and safety of Xinnaoning Capsule in the treatment of chronic stable angina pectoris (Qi stagnation and blood stasis syndrome)

3. Experimental design

3.1 Integral test design

The design adopted a placebo parallel control, randomized, double-blind, multi-center clinical research design method.

(1) Multi-center: This multi-center clinical study is expected to be carried out in Beijing, Shanghai, Shanxi and Tianjin.

(2) Random: block random method. SAS 9.1.3 statistical software was used to generate random number grouping table according to the number of cases allocated and random proportion of participating units.

(3) Double blindness: the appearance of the control drug is the same as that of

the test drug; the researchers who did not participate in the clinical research compiled the blindness of the research drug according to the randomized distribution table generated; according to the standardized operation steps of the double blindness clinical research, the test drug and the corresponding simulator were repackaged and distributed (including emergency letters).

(4) Control: placebo control. The purpose of this clinical trial is to evaluate the efficacy of Xinnaoning Capsule in the treatment of stable angina pectoris, which can reflect its "absolute" efficacy and safety, so the placebo control is used in this trial. For well-executed clinical trials, placebo-controlled trials can reliably prove the efficacy of research drugs, unlike non-inferiority design trials, which need to introduce the hypothesis of external efficacy sensitivity and test sensitivity; secondly, placebo-controlled clinical trials can clearly study the absolute efficacy of drugs; thirdly, they can better differentiate between non-inferiority design trials. Good events are caused by drugs or by some potential diseases or other factors; fourthly, they are more efficient and require a smaller number of subjects than any other parallel controlled study; fifthly, they can reduce the degree of disease improvement expected by the subjects and clinical researchers, and increase the ability to detect and study the true efficacy of drugs.

All subjects in this study received basic treatment routinely. Placebo use did not affect the normal treatment of subjects, which met the ethical requirements.

In the experiment, remedial measures such as nitroglycerin (uniformly provided by the applicant) will be given after the attack of angina pectoris. Diary cards and exercise manual of coronary heart disease will be issued during the clinical trial. Researchers should strengthen the observation of the number of attacks of angina pectoris and the dosage of nitroglycerin. The rights and interests of the subjects will be guaranteed and meet the ethical requirements.

Usage: When angina pectoris patients attack, take one tablet under the tongue, and repeat one tablet every 5 minutes until the pain relieves. If the pain persisted after a total of 3 tablets in 5 minutes, the subjects were immediately treated.

(5) Sample size: 120 cases in the experimental group and 120 cases in the control group.

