5.1 Administration method

The course of treatment was 14 weeks, including 2 weeks of introduction and 12 weeks of double blind treatment.

Introducing period: 2 weeks, time window (+2 days).

Introducing drug regimen: Both groups were given Xinnaoning capsule Simulator 3 capsules per time, 3 times per day, orally, after meals.

Course of treatment: 12 weeks, time window (+4 days).

Drug regimen for treatment period:

Test group: Xinnaoning capsule 3 capsules per time, 3 times per day, oral, after meals.

Control group: Xinnaoning capsule Simulator 3 tablets per time, 3 times per day, oral, after meals.

Basic treatment: During the introduction and treatment period, the experimental group and the control group could use antiplatelet drugs, angiotensin converting enzyme inhibitors (ACEI) or angiotensin II receptor antagonists (ARB), statins lipid-lowering drugs, calcium antagonists, beta-blockers, long-acting nitrates and other drugs without changing the original dosage. Nitroglycerin 0.5 mg can be administered sublingually, and the times and dosage of medication can be recorded in detail.

Sports regulations: 3-5 times a week, each lasting 30-40 minutes, 6.5-7.5 kilometers a week. See Annex 1 for details.

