5.9 Regulations on combined use of drugs

1. In addition to experimental medication, nitroglycerin tablets can be used to alleviate symptoms when angina attacks. For drugs already used to treat coronary heart disease before inclusion, such as antiplatelet drugs, angiotensin-converting enzyme inhibitors (ACEI) or angiotensin II receptor antagonists (ARB), statins, calcium antagonists, beta-blockers and long-acting nitrates, the original varieties and dosages can be continued without adjustment. During the study period, it is forbidden to add any other Chinese and Western medicines which have therapeutic effects on angina pectoris of coronary heart disease.

2. For the original and emerging diseases requiring drug treatment, the drug combination should be recorded in the medical record and CRF in detail, including the generic name of the drug, dosage and method of administration, the starting time of drug use and the reasons for its use.

6. Observation items

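### The rescue nitroglycerin rule asks for three tablets in 5 minutes, which its own 5-minute spacing makes impossible

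*Protocol*

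**What the plan says.** Section 3.1 of the protocol (Integral test design, under the placebo-control item) describes nitroglycerin as the remedy for angina attacks during the trial, supplied uniformly by the applicant. Its usage paragraph makes two statements, one directly after the other.

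- Spacing: the subject is to "take one tablet under the tongue, and repeat one tablet every 5 minutes until the pain relieves".
- Escalation: "If the pain persisted after a total of 3 tablets in 5 minutes, the subjects were immediately treated".

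Rescue nitroglycerin is also mentioned in these places:

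- Section 5.1 (Administration method) gives a dose and a recording duty: "Nitroglycerin 0.5 mg can be administered sublingually, and the times and dosage of medication can be recorded in detail".
- Section 5.9 (Regulations on combined use of drugs) gives a permission: "In addition to experimental medication, nitroglycerin tablets can be used to alleviate symptoms when angina attacks". The Combined medication row of the Abstract says the same.

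None of these gives an interval between tablets, a maximum number per attack, or a time at which to escalate.

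**The concern.** The two sentences in section 3.1 cannot both be followed as written. The first fixes the interval between tablets. The second requires three tablets inside a period no longer than one such interval.

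The second sentence matters because it carries the only limit in the instruction. Taken alone, the spacing sentence has no stop, since tablets continue until the pain goes. The three-tablet count and the move to immediate treatment appear only in the sentence with the wrong time. No other section gives a time for escalating care within an attack.

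Rescue use will be routine in this trial. Section 4.6 requires more than two attacks a week at entry, and section 3.1 cites the rescue provision when it says that subjects' interests are protected under placebo.

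What is at stake is the clarity of a safety instruction. Nitroglycerin consumption enters the angina score in section 4.3 and is a secondary indicator in section 6.2.2, but this wording is not claimed to change tablet intake, the primary score, sample size, alpha or power.

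**Working it through.** **Inputs, all from section 3.1**

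- First tablet at onset of the attack: time 0.
- Interval between tablets: 5 minutes.
- Count at which care escalates: 3 tablets.
- Stated window for that count: 5 minutes.

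**Step 1: tablet times under the spacing rule.** Tablet *k* is taken at 5 × (*k* − 1) minutes.

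| Tablet | Taken at | Its 5-minute interval ends at |
|---|---|---|
| 1 | 5 × 0 = 0 min | 5 min |
| 2 | 5 × 1 = 5 min | 10 min |
| 3 | 5 × 2 = 10 min | 15 min |

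**Step 2: try to reproduce the stated figure.** By 5 minutes, counting both ends of the window, the subject has taken the tablets due at 0 and 5 minutes. That is 2, not 3, so the stated figure cannot be reproduced. Three tablets within 5 minutes would need a spacing of at most 5 / 2 = 2.5 minutes, half the spacing prescribed.

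**Step 3: size of the discrepancy.**

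- To the moment the third tablet is taken: 10 − 5 = 5 minutes too short.
- To the end of the third tablet's interval: 15 − 5 = 10 minutes too short.

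The first figure follows from the text alone. The second assumes a 5-minute wait after the third tablet, which the protocol does not state.

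**Step 4: readings that would remove the conflict.**

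| Possible intended meaning | Resulting escalation time |
|---|---|
| Three tablets in total, at 5-minute intervals | 10 minutes or later; wait after the third tablet not stated |
| Pain persists 5 minutes after the third tablet | 10 + 5 = 15 minutes |
| Three tablets within 15 minutes | 15 minutes |

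The last two give the same time. The first leaves the wait after the third tablet open. The printed wording expresses none of them.

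**Step 5: look for a correction elsewhere.** The Abstract and sections 5.1 and 5.9 give no timing. Section 4.8.1 provides for emergency measures when attacks become more frequent, longer or more painful, but gives no time within an attack. The exercise manual (Enclosure 1) tells the subject to stop and rest on chest pain and gives no nitroglycerin rule. Nothing in the document settles the point.

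**The case against.** The strongest reply is that this is a translation artefact with little practical effect. The English text is visibly a rough translation: stray Chinese text remains in sections 8.1.1 and 8.1.2, and phrases are garbled elsewhere. The original may well have meant tablets at 5-minute intervals, or 5 minutes after the third tablet. Neither reading would conflict with the spacing sentence.

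The trigger also works without its time phrase: three tablets, pain still present, treat. The spacing rule already places the third tablet at 10 minutes, so little is left to guess. If the 5-minute figure influenced anyone, it would point towards earlier escalation rather than delay. Finally, the diary cards and other subject materials are not shown, so it is unknown whether any subject would read the faulty phrase.

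Much of this stands. The count is usable, the only open question for a site is how long to wait after the third tablet, no delay in care has been shown, and the source-language protocol may be correct. These points limit the weight of the finding but do not remove it. The printed time is impossible under the sentence before it, and the reader has to supply the correction.

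**Conclusion.** The concern holds. The escalation window in section 3.1 is wrong as written: at most 2 of the 3 tablets fit inside it. It is 5 minutes short of the third tablet and, if a 5-minute wait after that tablet is assumed, 10 minutes short of the decision point.

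Confidence is high for the English text, since the result needs only the two adjacent sentences and simple arithmetic. Whether the source-language protocol has the same error cannot be judged from this document. The 15-minute figure is a proposal that fits the spacing, not something the protocol states.

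The sponsor should correct this because it is the only stop-and-treat rule for an attack. It has no bearing on the design or the statistical analysis.

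**What to change.** Keep the 5-minute spacing, state the cap of three tablets, and replace the 5-minute window with one that fits. Suggested wording:

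> At the onset of an attack, place one nitroglycerin tablet under the tongue. If pain continues, take a second and then a third at 5-minute intervals, with no more than three tablets per attack. If pain is still present 5 minutes after the third tablet (15 minutes after the first), immediate treatment is required.

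The clinical team should confirm the wait after the third tablet and check the sentence against the source-language text. The diary cards and any other subject instructions should then be checked for the same wording.

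The cost is one corrected sentence and that check. Section 14 already sets out how protocol modifications are handled, and no design or analysis change follows.
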